6.2 SUMMARIES OF CONDUCT OF STUDY

Enrollment, study treatment administration and discontinuation from the study will be summarized by treatment arm. The incidence of study treatment discontinuation for reasons other than disease progression will be assessed.

6.3 SUMMARIES OF TREATMENT GROUP COMPARABILITY

Demographic variables, stratification factors, and other baseline characteristics will be summarized by treatment groups.

Descriptive summaries of continuous data will present the group mean, standard deviation, median, minimum and maximum. Descriptive summaries of discrete data will present the category counts as frequencies and percentages.

6.4 EFFICACY ANALYSES

The primary and secondary efficacy analyses will include all randomized patients, with patients grouped according to the treatment assigned at randomization.

6.4.1 Primary Efficacy Endpoint

The primary efficacy endpoint is PFS, defined as the time from randomization to the first occurrence of disease progression, as determined by investigator review of tumor assessments using RECIST v1.1 or death on study from any cause. The primary efficacy analyses will be performed on all randomized patients as well as on patients with *ESR1* LBD mutations detected in circulating cell-free DNA, with patients allocated to the treatment arm assigned at randomization.

For patients without disease progression or death as of the clinical data cutoff date, their PFS will be censored at the time of last tumor assessment (or censored at the date of randomization, if no tumor assessment was performed after the baseline visit). For patients who start other anti-cancer treatment prior to the documented PFS event, the primary PFS analysis will include PFS events after other anti-cancer treatment. PFS

sensitivity analysis will be performed, censoring PFS on the last tumor assessment prior to starting other anti-cancer therapy.

The two-sided log-rank test stratified by the stratification factors will be used as the primary analysis. The Kaplan-Meier approach will be used to estimate median PFS for each treatment arm. Cox proportional hazards models stratified by the stratification factors will be used to estimate a hazard ratio and its 90% CI. The results from the unstratified analysis will also be provided.

Exploratory analysis for PFS may be performed on patient subgroups by demographic disease characteristics.

6.4.2 Secondary Efficacy Endpoints

6.4.2.1 Objective Response Rate

The analysis of ORR will only include patients who have measurable disease at baseline (and will thus exclude patients with bone-only disease). An estimate of the response rate and its 90% CI will be calculated using the Blyth-Still-Casella method for each treatment arm. Response rate in the treatment arms will be compared using the stratified Mantel-Haenszel test. CIs for the difference in ORRs between the two arms will be determined using the normal approximation to the binomial distribution.

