1.2.2 Summary of Phase I Clinical Data

GDC-0810 is currently being studied in Study GO29642 (formerly known as ARN-810-001), a Phase Ia/Ib/IIa open-label, dose-finding, safety, pharmacokinetic (PK), and proof-of-concept trial of single-agent GDC-0810 *and in combination with palbociclib or luteinizing hormone-releasing hormone (LHRH) agonist in postmenopausal women with locally advanced or metastatic ER+ breast cancer.*

As of 1 October 2014, enrollment in the Phase I dose-escalation portion of Study GO29642 was completed with 41 patients enrolled at doses from 100 mg to 800 mg. Nine dose-escalation cohorts of 3–6 patients each were enrolled. Patients received between 100 and 800 mg total daily dose, given once daily (QD) or divided twice daily (BID), with fasting and without fasting. As of 15 April 2016, a total of 39 patients have discontinued the study: 36 (88%) due to disease progression, 1 (2%) due to non-treatment-related cardiac arrest, 1 (2%) due to treatment-related nausea, and 1 (2%) withdrew consent due to ongoing diarrhea. At the time of the data cutoff (15 April 2016), with a median follow-up of 4 months (range: 1–26 months), 16 of 41 (39%) patients were on study \geq 6 months; among those patients previously treated with fulvestrant, 6 of 17 (35%) were on study \geq 6 months. In addition, robust ER target engagement across all doses was demonstrated by 18 F-fluoroestradiol positron emission tomography (FES-PET) scans, and there were two confirmed partial responses (PRs) as of the data cutoff.

As of 15 April 2016, 1 of 6 patients had experienced a dose-limiting toxicity (DLT) of Grade 3 diarrhea in the 800-mg QD fasting cohort, which resolved with dose modification and antidiarrheal therapy. A maximum tolerated dose (MTD) was not determined. However, given the high proportion of gastrointestinal (GI) adverse events, doses of 800 mg were deemed intolerable in the clinical setting of breast cancer. A recommended Phase II dose (RP2D) of 600 mg QD administered under fed conditions (i.e., 30 minutes after eating a meal) was selected based on the overall safety, tolerability, and PK profile of GDC-0810.

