1.4 STUDY RATIONALE AND BENEFIT-RISK ASSESSMENT

Fulvestrant is an accepted, standard-of-care therapy for the patient population targeted by this study (see Section 4.1.1). In a study of fulvestrant in a population with breast cancer who had previously received endocrine therapy, the most common adverse events reported were injection-site pain (11.6%), nausea (9.7%), and bone pain (9.4%). Fulvestrant should be used with caution in patients with hepatic impairment. Because fulvestrant is administered intramuscularly, it should also be used with caution in patients with bleeding diatheses, thrombocytopenia, or anticoagulant use.

GDC-0810 is a potent, orally bioavailable ER- α antagonist that is being developed for the treatment of postmenopausal women with ER+ advanced or MBC whose disease has recurred or progressed following treatment with hormonal therapy. In murine MCF-7 xenograft models, GDC-0810 has demonstrated robust tumor regression in both tamoxifen-sensitive and tamoxifen-resistant models, with superior tumor growth inhibition than fulvestrant at clinically relevant exposures. GDC-0810 is currently being tested in a Phase I/IIa study in postmenopausal women with ER+/human epidermal growth factor receptor 2 (HER2)–advanced and MBC.

As of 15 April 2016, a total of 41 patients had been treated with GDC-0810 doses ranging from 100–800 mg. Robust ER target engagement across all doses was demonstrated by FES-PET scans. Sixteen of 41 (39%) evaluable patients in this heavily pre-treated patient population (median 4 prior systemic treatments, range 1–14) had total time on study >6 months, which is comparable to the 24-week clinical benefit rate (CBR) of 32%–42% achieved by fulvestrant in patients with ER+ advanced or MBC after one prior endocrine therapy (Chia et al. 2008; Di Leo et al. 2010; Johnston et al. 2013). Additionally, 2 patients with ESR mutations have achieved a partial response by Response Evaluation Criteria in Solid Tumors (RECIST) 1.1 since the data cut at GDC-0810 doses of 300 mg BID and 400 mg BID.

At 600 mg by mouth (PO) daily under nonfasting conditions, GDC-0810 *has been well tolerated with most adverse events from Grade 1 to 2 in severity (see Section 1.2.2 for a summary of clinical safety).*

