2. OBJECTIVES

The development of GDC-0810 has been halted and enrollment discontinued; therefore, the primary objectives will not be met.

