4.5.10 Assay Methods

4.5.10.1 Mutational Analysis for *ESR1*

Somatic mutations in the LBD of the *ESR1* gene confer ligand independence and are found in approximately 40% of metastatic breast cancers but are rare in primary breast cancers. ctDNA obtained from plasma offers a robust mutation detection alternative to tissue that can be collected with less inconvenience and risk to patients, particularly those with bone metastases that are difficult to biopsy. Quantitative real-time PCR (qRT-PCR) assays or NGS assays designed to interrogate the LBD of *ESR1* offer a sensitive and quantitative method to detect mutations from ctDNA. DNA will be extracted from plasma samples and subjected to NGS and/or qRT-PCR assays that detect the wild-type allele, as well as mutations that include, but are not limited to, the following amino acid changes: D538(G), Y537(S, N, C), E380(Q), L536(Q, H, P, R), S463P and P535H. Assays may also be run on metastatic tumor tissue if such tissue is available. Assays from all samples will be run in a central laboratory on analytically validated NGS and/or qRT-PCR platforms, and mutation calls will be made using appropriate cutoffs and automated software. The information about the spectrum and the prevalence of *ESR1* mutations may help with the development of a companion diagnostic for GDC-0810.

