6. STATISTICAL CONSIDERATIONS AND ANALYSIS PLAN

Primary and secondary efficacy analyses will include all randomized patients, with patients allocated to the randomized treatment arm. In addition to the all-randomized patient population (the ITT population), analysis of PFS, ORR, and CBR will be repeated in the patient subsets defined by their *ESR1* mutation status.

Safety analyses will include all patients who received at least one dose of the study treatment, with patients allocated to the treatment arm associated with the regimen actually received.

There will be no adjustments made for multiple comparisons when analyzing the primary and secondary endpoints.

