6.1 DETERMINATION OF SAMPLE SIZE

The trial is designed to evaluate the clinical activity and safety of GDC-0810 compared with fulvestrant in patients with ER-positive locally advanced or MBC. It is for hypothesis generation, and is not powered to detect minimum clinically meaningful difference between treatment arms.

A total of approximately 152 patients will be enrolled in this study. It is assumed that the median duration of PFS in the fulvestrant control arm is 5.5 months and 8.5 months in the GDC-0810 arm. The final analysis of all randomized patients will be triggered by the occurrence of approximately 95 PFS events, which is expected to occur 26 months after the first patient is randomized. [Table 4](#) shows expected probabilities of observing a hazard ratio of less than 0.5, 0.6 and 0.7 in the final analysis in all randomized patients under varying assumptions for the true underlying hazard ratio. Note that formal hypothesis testing is limited. Rather than testing treatment differences at a statistically significant type I error level of 5%, 90% confidence intervals (CI) for the hazard ratio will be calculated.

At a target hazard ratio of 0.6, the corresponding 90% CI based on 95 PFS events is (0.43, 0.84) which is considered to provide meaningful precision.

Table 4 Expected Probability of Observing a Hazard Ratio of <0.5, <0.6, or <0.7 in the Final Analysis (All Patients)

True HR	95 PFS Events in ITT Population		
	Observed HR < 0.50	Observed HR < 0.60	Observed HR < 0.70
0.4	0.86	0.98	0.99
0.5	0.50	0.81	0.95
0.6	0.19	0.50	0.77
0.7	0.05	0.23	0.50
0.8	0.01	0.08	0.26

HR=hazard ratio; ITT=intent to treat; PFS=progression-free survival.

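### In the *ESR1*-mutant subset, the normal-approximation CI for the ORR difference is underspecified and off its inferred 90% level: on average about 2 points short if uncorrected, about 5 points over if continuity-corrected

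*Combined protocol and SAP*

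**What the plan says.** Section 6.4.2.1 restricts ORR to patients with measurable disease at baseline and treats the two intervals differently. For the single-arm rates: "An estimate of the response rate and its 90% CI will be calculated using the Blyth-Still-Casella method for each treatment arm". For the comparison: "CIs for the difference in ORRs between the two arms will be determined using the normal approximation to the binomial distribution". The second sentence gives no confidence level and does not say whether a continuity correction applies.

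Section 6 adds that "analysis of PFS, ORR, and CBR will be repeated in the patient subsets defined by their" *ESR1* mutation status. The comparison is therefore planned in a small subset, which is also a co-primary population for PFS (Section 2.1). Section 4.5.10.1 describes *ESR1* ligand-binding-domain mutations as "found in approximately 40% of metastatic breast cancers".

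The documents give no expected ORR for either arm and no expected share with measurable disease. Section 6.1 says of the trial: "It is for hypothesis generation, and is not powered to detect minimum clinically meaningful difference between treatment arms". Section 2 records "enrollment discontinued; therefore, the primary objectives will not be met"; the number actually enrolled is not stated.

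**The concern.** The normal-approximation interval for a difference in proportions is unreliable when arms are small and responders few. An arm with no responders contributes zero to the estimated variance, so the uncorrected interval is too short, or has no width at all. The section uses a small-sample method for each arm's rate and a large-sample one for the difference, where the same problem arises.

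Low response rates are plausible from the documents, though not established. Section 1.2.2 reports that "there were two confirmed partial responses (PRs) as of the data cutoff" among 41 Phase I patients, 2/41 = 4.9%. Section 1.4 says that "2 patients with ESR mutations have achieved a partial response" since the data cut. If those two are additional, which the text does not settle, the figure is 4/41 = 9.8%. Those patients were heavily pre-treated, and 41 is not a measurable-disease denominator, so rates here may be higher.

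At stake is how precise the between-arm ORR difference appears in the *ESR1*-mutant subset. Section 6.1 rests the primary comparison on 90% CIs rather than 5%-level testing, so readers are directed to intervals.

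**Working it through.** **The plan's own figure.** The plan states no precision for ORR. Its only stated interval is for the hazard ratio: exp(ln 0.6 ± 1.645 × 2/√95) = (0.43, 0.84), which reproduces Section 6.1.

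**Measurable patients per arm.** Inputs are 152 patients and 1:1 allocation (documents), 40% prevalence (Section 4.5.10.1, assumed to hold here) and 60-75% measurable (assumed).
- *ESR1*-mutant: 152 × 0.40 × 0.60 / 2 = 18.2 to 152 × 0.40 × 0.75 / 2 = 22.8.
- Non-mutant: 152 × 0.60 × 0.60 / 2 = 27.4 to 152 × 0.60 × 0.75 / 2 = 34.2.
- All patients: 152 × 0.60 / 2 = 45.6 to 152 × 0.75 / 2 = 57.

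**Intervals compared**, with z = 1.645 (90%, inferred from the single-arm sentence) and d = p1 − p2:
- Uncorrected Wald: d ± z √(p1q1/n1 + p2q2/n2).
- Continuity-corrected Wald: the same, widened by ½(1/n1 + 1/n2) on each side.
- Newcombe, from the Wilson limits (l, u) of each arm: lower d − √((p1 − l1)² + (u2 − p2)²), upper d + √((u1 − p1)² + (p2 − l2)²).

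**Exact coverage**, enumerating all outcome pairs of two independent binomials, n = 18 to 23 in each arm, nominal 0.90. True rates are assumed.

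| True rates | Wald, uncorrected | Wald, corrected | Newcombe |
|---|---|---|---|
| 10% vs 5% | 0.80-0.86 | 0.95-0.99 | 0.94-0.95 |
| 20% vs 5% | 0.83-0.89 | 0.95-0.97 | 0.90-0.93 |
| 20% vs 10% | 0.86-0.89 | 0.95-0.96 | 0.90-0.92 |
| 30% vs 10% | 0.87-0.90 | 0.94-0.95 | 0.90-0.92 |
| 10% vs 10% | 0.89-0.90 | 0.95-0.97 | 0.89-0.93 |
| 5% vs 5% | 0.93-0.95 | 0.98-0.99 | 0.94-0.98 |

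**Grid.** Both rates run from 5% to 30% in 1-point steps, at least 5 points apart: 231 pairs × 6 arm sizes = 1386 settings.
- Uncorrected Wald: mean 0.879, minimum 0.8046 (n = 18, 10% vs 5%); 43% of settings below 0.88, 2% below 0.85.
- Corrected Wald: mean 0.951.
- Newcombe: mean 0.910, minimum 0.889.

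**Direction of the misses.** At 10% vs 5% the true difference lies above the upper limit in 11-15% of trials with uncorrected Wald and in 3.5-3.7% with Newcombe; nominal is 5%.

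**Zero responders.** At 5% vs 5%, the chance that neither arm has a responder is 0.95^36 = 0.16 at n = 18 and 0.95^46 = 0.09 at n = 23. For 0/18 vs 0/18, uncorrected Wald gives (0, 0). The Wilson upper limit is 2.706/(18 + 2.706) = 0.131, so Newcombe gives (−0.13, 0.13).

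**Example with responders**, 2/18 vs 0/18: d = 0.111 and SE = √(0.111 × 0.889/18) = 0.074, so uncorrected Wald is (−0.01, 0.23). Newcombe is (−0.04, 0.29).

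**Other populations at full accrual.** Uncorrected Wald covers 0.87-0.90 in the non-mutant subset and 0.88-0.90 in all measurable patients. For CBR at 30-31 per arm, with rates of 32-42% (the range that Section 1.4 gives for fulvestrant), it covers 0.88-0.90.

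**Sensitivity at 10% vs 5%.** Prevalence 30% (14-17 per arm): Wald 0.75-0.79. Prevalence 50% (23-28 per arm): 0.86-0.88. Newcombe is 0.93-0.95 in both. At a 95% level: Wald 0.85-0.90, Newcombe 0.98-0.99. If only half of the 152 were enrolled (assumed; 9-11 per arm): Wald 0.69-0.74.

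**The case against.** The strongest objection is that the text does not commit to an uncorrected interval. A normal approximation can carry a continuity correction, and then there is no under-coverage. This stands: a reader might infer that the planned interval is certain to be too short, but the documents support only that it is too short on one reading and too wide on the other.

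A reader might also take 0.80-0.86 as the typical coverage. It is not. It belongs to the least favourable pair tried, 10% vs 5%, and the n = 18 value is the minimum of the whole grid. The typical shortfall is about 2 points, and at some rate pairs there is none. No ORR is given for either arm, so that pair cannot be presented as expected.

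Nor does the point reach the main ORR comparison at the planned size, where uncorrected Wald covers 0.88-0.90. The half-enrolment figures show the direction of the effect but are speculative.

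Two further points have weight. The Blyth-Still-Casella interval for each arm would be reported alongside and would show non-zero upper limits even with no responders, which softens the (0, 0) problem. And Newcombe is itself conservative at very low rates.

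What survives is that the sentence leaves level and correction open, and that Newcombe's mean coverage is closer to 0.90 than either reading of it.

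**Conclusion.** The concern holds as a minor point about the *ESR1*-mutant subset. Over the assumed grid, mean coverage departs from 0.90 by 0.900 − 0.879 = 0.021 below for uncorrected Wald, 0.951 − 0.900 = 0.051 above for corrected Wald, and 0.910 − 0.900 = 0.010 above for Newcombe.

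This rests on assumptions that the documents do not supply: the measurable share, the true response rates, the 90% level for the difference, and 40% prevalence in this population. It also takes the planned 152 patients. Enrollment has stopped, and if fewer were enrolled, the uncorrected interval would tend to perform worse.

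ORR is a secondary endpoint in a hypothesis-generating trial whose development has been halted. No decision rule depends on this interval.

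**What to change.** Replace the last sentence of Section 6.4.2.1 with wording such as: *The between-arm difference in ORR will be reported with a 90% CI by the Newcombe (Wilson score) method, without continuity correction, in all patients with measurable disease and in each ESR1 subset.* This fixes the method, the level and the correction together. Section 6.4.2.3 (CBR) can stay as it is.

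The cost is one sentence and a standard software option. Newcombe intervals are on average wider than uncorrected Wald, by 23-30% at 10% vs 5%, 6-7% at 20% vs 10% and 2-3% at 30% vs 10%, and they are conservative at very low rates (0.94-0.98 at 5% vs 5%). The Miettinen-Nurminen score interval would also improve on uncorrected Wald, but its minimum coverage over the same grid is lower (mean 0.895, minimum 0.860).

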6.4.2.2 Duration of Objective Response

DOR is defined as the time from first observation of an objective response until first observation of disease progression as assessed by the investigator according to RECIST v1.1 or death from any cause. The analysis of DOR will include only patients who achieved an objective response.

DOR will be estimated using the Kaplan-Meier methodology, with patients grouped according to the treatment arm assigned at randomization. Comparisons between treatment arms using stratified and unstratified log rank test will be made for descriptive purposes. Because the determination of DOR is based on a nonrandomized subset of all patients, formal hypothesis testing will not be performed.

6.4.2.3 Clinical Benefit Rate

CBR is defined as the percentage of patients who experience a CR, PR, or SD lasting for at least 24 weeks since randomization. An estimate of CBR and its 90% CI will be calculated using the Blyth-Still-Casella method for each treatment arm. The CBRs in the treatment groups will be compared using the stratified Mantel-Haenszel test. CIs for the difference in CBR between the two arms will be determined using the normal approximation to the binomial distribution.

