- Inability, in the opinion of the investigator, to comply with study and follow-up procedures

Length of Study

The enrollment duration is projected to be approximately 22 months after the first patient is enrolled. The last PFS event for the primary PFS analysis is projected to occur approximately 26 months after the first patient is enrolled.

End of Study

The end of this study is defined as the date when the last patient, last visit occurs, GDC-0810 drug supply is exhausted, or when the Sponsor decides to stop the study.

Outcome Measures

Primary Efficacy Outcome Measures

The primary efficacy outcome measures for this study, for all patients as well as the subset of patients with *ESR1* mutations, are as follows:

- PFS, defined as the time from randomization to the first occurrence of disease progression as determined by the investigator per RECIST v1.1 or death from any cause on study, whichever occurs first

Secondary Efficacy Outcome Measures

The secondary outcome measures for this study are the following:

- OS, defined as the time from randomization to the time of death from any cause
- Objective response (PR plus complete response [CR]) as determined by the investigator per RECIST v1.1
- DOR, defined as the time from the first occurrence of a documented objective response until first observation of disease progression, as determined by the investigator per RECIST v1.1, or death from any cause on study, whichever occurs first
- Clinical benefit, defined as PR, CR, or stable disease (SD), lasting for at least 24 weeks from the time of randomization

Safety Outcome Measures

The safety and tolerability of GDC-0810 will be assessed using the following:

- The incidence, nature, and severity of adverse events reported during the adverse event reporting period, graded according to the National Cancer Institute Common Terminology Criteria for Adverse Events version 4.0 (NCI CTCAE, v4.0)
- Incidence, nature and severity of serious adverse events
- Incidence of adverse events leading to study treatment discontinuation, modification or interruption
- Clinically significant changes in vital signs, physical findings, and clinical laboratory results during and following GDC-0810 or fulvestrant administration during the adverse-event reporting period

Pharmacokinetic Outcome Measures

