Enrollment in Study GO29689 has been discontinued; therefore, no further patients will be enrolled in this study. Any patient currently enrolled in Study GO28689 experiencing clinical benefit may continue to receive GDC-0810 as a single agent or fulvestrant until disease progression (as assessed by the investigator based on radiographic findings or clinical symptoms), unmanageable toxicity, patient withdrawal of consent, GDC-0810 drug supply has been exhausted, or the Sponsor terminates the study. All patients who are discontinued from study treatment will return for a study drug discontinuation visit within 30 days after the last dose of study treatment and will be followed for adverse events for at least 28 days after the last dose of study treatment.

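### The 24-week clinical benefit rate is a crude percentage of all randomized patients, with no rule for those followed for less than 24 weeks

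*Combined protocol and SAP*

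**What the plan says.** Section 6.4.2.3 gives the definition: "CBR is defined as the percentage of patients who experience a CR, PR, or SD lasting for at least 24 weeks since randomization". It estimates each arm's rate with a Blyth-Still-Casella 90% interval, compares the arms by a stratified Mantel-Haenszel test, and uses the normal approximation for the difference.

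The denominator comes from Section 6.4: "The primary and secondary efficacy analyses will include all randomized patients". The opening of Section 6 says the same. Where a narrower set is meant, the plan names it, as in Section 6.4.2.1: "The analysis of ORR will only include patients who have measurable disease at baseline". CBR has no such restriction.

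On timing, the synopsis (Length of Study) says: "The enrollment duration is projected to be approximately 22 months after the first patient is enrolled", and "The last PFS event for the primary PFS analysis is projected to occur approximately 26 months after the first patient is enrolled". Section 6.1 makes the final analysis event-driven: "triggered by the occurrence of approximately 95 PFS events, which is expected to occur 26 months after the first patient is randomized".

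Censoring rules are written for PFS (Section 6.4.1) and OS (Section 6.8). None is written for CBR. The current version also records in Section 3.1: "Enrollment in Study GO29689 has been discontinued; therefore, no further patients will be enrolled in this study".

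**The concern.** CBR needs 24 weeks of observation after randomization before a patient with stable disease can qualify. On the projected timeline the last patient has about 4 months. The methods in Section 6.4.2.3 need a yes or no for every patient and cannot censor. A patient who is event-free at month 4 when the data are cut has not shown 24 weeks of benefit, so a crude percentage over all randomized patients scores her as a no. Any other handling needs a rule that the plan does not contain.

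At stake is a downward bias in each arm's CBR and its 90% CI, caused by the calendar and not by the disease, with some shrinkage of the difference between arms. Leaving the rule unwritten also means the choice could be made after results are known, in an open-label trial in which Section 4.2 leaves the sponsor unblinded.

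**Working it through.** **The plan's own figure.** Section 6.1 gives a 90% CI of 0.43 to 0.84 for a hazard ratio of 0.6 with 95 events. exp(ln 0.6 ± 1.645 × 2/√95) = 0.428 to 0.841, which agrees. Tables 4 and 5 also reproduce, each cell within 0.01. The 95 events matter here because they set the cutoff.

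**Inputs from the documents.** 152 patients, 1:1; median PFS 5.5 months (fulvestrant) and 8.5 months (GDC-0810); enrollment 22 months; cutoff 26 months.

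**Assumptions.** The documents give no accrual shape or dropout rate. I take exponential PFS, treat clinical benefit as being event-free at 24 weeks, and use two accrual shapes: uniform, and ramped with cumulative share (t/22)².

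**Step 1: follow-up of the last patient.**
- Required: 168 days / 30.44 = 5.52 months.
- Available: 26 − 22 = 4 months = 17.4 weeks, which is 6.6 weeks short.

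**Step 2: patients who cannot reach 24 weeks by month 26.** These are patients randomized after month 26 − 5.52 = 20.48.
- Uniform: (22 − 20.48)/22 = 6.9%; × 152 = about 10.5 patients.
- Ramped: 1 − (20.48/22)² = 13.3%; × 152 = about 20.3 patients.

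**Step 3: how many of these are undetermined.** Some will have progressed before the cutoff and are true failures. With λ = ln 2/median and uniform accrual, the number still event-free per arm is (76/22) × (exp(−4λ) − exp(−5.52λ))/λ.
- Fulvestrant (λ = 0.126): 2.9. GDC-0810 (λ = 0.0815): 3.6. Total about 6.4.
- The same calculation with ramped accrual gives 5.6 + 6.9, or about 12.5.

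**Step 4: effect on CBR if short-follow-up patients count as no benefit.** The 24-week rates are exp(−5.52λ) = 49.9% and 63.8%, a difference of 13.9 points. Multiply each by the share with full follow-up.

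| Accrual | Share with 24 weeks | Fulvestrant | GDC-0810 | Difference |
|---|---|---|---|---|
| All followed 24 weeks | 100% | 49.9% | 63.8% | 13.9 |
| Uniform | 93.1% | 46.4% | 59.4% | 12.9 |
| Ramped | 86.7% | 43.2% | 55.3% | 12.0 |

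**Step 5: sensitivity to the event trigger.** The cutoff follows the events, not the calendar. With uniform accrual and no dropout, the stated medians give about 111 events at month 26, and the 95th falls at about month 22.7. At that cutoff about 33 patients (22%) would be short of 24 weeks, and the rates would be 38.9% and 49.7%, a difference of 10.8 points. A 95th event near month 26 needs ramped accrual (about 97 events at month 26) or, with uniform accrual, about 29% dropout a year.

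**Step 6: cutoff at which nobody is short.** 22 + 5.52 = 27.5 months, about 1.5 months after the projected date.

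**The case against.** **The plan never calls these patients failures.** A reader might infer a stated failure rule. None exists, and the text is silent. What stands is that the literal calculation produces that result, so the defect is an omitted rule whose default is biased.

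**The 22- and 26-month timeline no longer operates.** This stands. Enrollment has been halted, Section 2 says the primary objectives will not be met, and neither actual enrollment nor a new cutoff is given. A reader might infer that stopping early makes the share larger. The documents do not support that. Section 3.1 lets patients with clinical benefit continue treatment, so those event-free at the halt could pass 24 weeks, and a cutoff six months after the last randomization would leave nobody short. Equally, Section 3.2 allows the study to end on drug exhaustion or sponsor decision, so 24 weeks is not assured. Section 6.4.2.3 remains in force.

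**The comparison is hardly affected.** This largely stands. Both arms face the same truncation. A shift of 1 to 2 points, or about 3 with the early trigger, is small against a 90% CI half-width of about 13 points: 1.645 × √(0.499 × 0.501/76 + 0.638 × 0.362/76) = 0.131. Section 6.1 describes the trial as hypothesis-generating. The weight therefore falls on the absolute rates.

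**Section 1.4 might be read as a benchmark.** It cites a fulvestrant CBR of 32% to 42%, and a reader might infer that this trial's CBR will be judged against it. That section compares Phase I time on study with published rates as background. It sets no threshold here, and this trial has its own randomized fulvestrant arm. The range does show that the PFS proxy may run high: at a true rate of 32% to 42%, the 6.9% shortfall costs 2.2 to 2.9 points.

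**A new denominator would be chosen after unblinding.** Sections 5.1 and 5.1.2 record that the study team is unblinded. This stands as a reason to use a rule fixed by date and to keep the all-randomized figure visible. Kaplan-Meier PFS under Section 6.4.1 already handles truncation, but it does not repair the CBR estimate.

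**Conclusion.** The concern holds as an omission with a predictable direction. Followed as written, Section 6.4.2.3 counts event-free patients with less than 24 weeks of follow-up as having no benefit, and so understates CBR in both arms.

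On the retained projection, about 7% to 13% of patients are short of 24 weeks and about 4% to 8% (6.4/152 to 12.5/152) are undetermined. The loss is modest for each arm's rate and minor for the difference. It grows if the 95 events arrive before month 26. These sizes rest on exponential PFS at the planned medians, the two assumed accrual shapes, and PFS at 24 weeks as a stand-in for CBR.

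For the trial as it stands after Version 2, the documents do not allow a count. It may be anywhere from zero upward, depending on the cutoff.

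**What to change.** In Section 6.4.2.3, do one of the following:

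- Base CBR on patients randomized at least 24 weeks before the clinical data cutoff. Membership depends only on the calendar date, so it is independent of outcome. On the retained projection this keeps about 141 to 142 of 152 patients with uniform accrual, or about 132 with ramped accrual.
- Set the CBR cutoff at least 24 weeks after the last randomization, which keeps everyone.

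In either case, report the all-randomized figure as supportive, and record that the rule was added after the study team was unblinded.

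The first option costs one sentence, a somewhat smaller denominator and a wider CI, and needs no new data. The second costs time: about 1.5 months on the projection. With enrollment closed, it may cost nothing if the actual cutoff already falls late enough.
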